4.1 Demographics and baseline characteristics

Demographic and baseline characteristic including: age, race and ethnicity, menopausal status, mammographic breast density, palpability, cancer histologic type, tumor size, node positive patients, and tumor receptor status (ER/PR/HER2), and baseline body mass index (BMI) calculated from weight and height will be summarized for the study sample. Statistics for continuous variables will include mean, median, standard deviation (SD), minimum, maximum and sample size for the overall sample and grouped by control and device arms, and two-sided 95% CI of the mean difference between (control and study arms). Binary variables will be described with frequencies and percentages for the overall sample. Demographic and baseline characteristics will be summarized by overall using descriptive statistics for analysis populations.

4.2 Residual cancer removal (co-primary endpoint)

The null hypothesis is that the true percentage of patients in whom at least one LUM-guided shave removed after the SOC procedure contains cancer as confirmed by pathology examination is smaller than or equal to 3%:

$$H_0: p \leq 3\%$$

LUMICELL CONFIDENTIAL

This document is confidential. Do not disclose or use except as authorized.

The alternative hypothesis is that the true percentage of patients in whom at least one LUM-guided shave removed after the SOC procedure contains cancer as confirmed by pathology examination is larger than 3%:

$$H_A: p > 3\%$$

where p is the true percentage of patients in whom at least one LUM-guided shave removed after the SOC procedure contains cancer as confirmed by pathology examination.

The hypothesis will be tested using an exact Binomial test at a one-sided significance level of 2.5%. The true proportion p will be estimated along with a two-sided 95% exact confidence interval. The null hypothesis H_0 is rejected if the lower bound of the confidence interval for removal of residual cancer sensitivity is larger than the performance goal of 3%.

Performance goal selection for removal of residual cancer endpoint

To choose the success criteria for the proportion of patients who have residual cancer found in at least one LUM-guided shave, we used published results for estimates of local recurrence before and after adjuvant radiation, assuming that most local recurrences are a consequence of unresected cancer during the initial surgery. The meta-analysis conducted on approximately 28,000 patients to support the consensus guideline for margin in 2014 from SSO-ASTRO, reported an overall recurrence rate of 5.3% for patients undergoing lumpectomy and receiving whole breast radiation therapy (including patients with positive and negative margins) [1]. Other investigators have published local recurrence rates for patients with negative margins at 10.2% without a radiation boost, while 6.2% for those with radiation boosts [3]. Based on this data, we estimate that radiation addresses approximately 50% of residual cancer, but not all. Our Phase C results shows a proportion of 26/230 or 11.3% [95% CI: 7.5%-16.1%], supporting the performance goal selection of this endpoint.

Sample size for testing residual cancer removal

Our preliminary analysis of the Phase C exploratory data indicated that LUM detected residual cavity cancer in 11% of patients (26/230). To power the study, we are using a slightly more conservative assumption of a ~9% true percentage of patients in whom at least one therapeutic shave has cancer confirmed by pathology. With this assumption, enrolling 220 evaluable subjects, a binomial exact test for proportions at a one-sided significance level of 2.5%, will have 90% power to declare the percentage of patients in whom at least one therapeutic shave has cancer confirmed by pathology to be larger than 3%.

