Our preliminary analysis of the Phase C exploratory data indicated that LUM detected residual cavity cancer in 11% of patients (26/230). To power the study, we are using a slightly more conservative assumption of a ~9% true percentage of patients in whom at least one therapeutic shave has cancer confirmed by pathology. With this assumption, enrolling 220 evaluable subjects, a binomial exact test for proportions at a 1-sided significance level of 2.5%, will have 90% power to declare the percentage of patients in whom at least one therapeutic shave has cancer confirmed by pathology to be larger than 3%.

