15.3.3 Study sample size, event-driven design, and overall study power

The pivotal study is powered based upon targeting success for the three co-primary endpoints as outlined above. The efficacy endpoints will be assessed in the patients who undergo LUM-guided imaging (not the 1/10th of subjects randomized to the control arm).

Based on Phase C data, it is expected that 268 patients will provide the necessary 70 truth standard positive events to power for sensitivity. Also, based on Phase C data, it is expected that 152 patients will provide the necessary 1021 truth standard negative events to power for specificity. To power for the removal of residual cancer endpoint, approximately 220 patients are required. Thus, the size of this study is driven by the necessary number of truth standard positive events.

Adding 15% to the sample size of 268 patients to include subjects in the control arm and some expected data loss, it is estimated that 310 total patients will be needed for the pivotal study. However, given the uncertainty of translating the number of truth standard positive events to actual number of patients, the pivotal trial is planned as an event-driven clinical study. Patients will be enrolled until 70 truth standard positive events are reported, up to a maximum of 350 patients. The number of truth standard positive events will be counted based on the truth standard hierarchical approach from Figure 6. Counting of these events will be conducted via software programming to read from the electronic data capture system; no endpoints will be calculated at that time. Results

from the event counting process will be accessible to the DSMB which will then inform Lumicell personnel on whether the targeted number of events has been reached or if enrollment needs to continue.

At this sample size, the power for the sensitivity endpoint is 90%, for specificity is 99% and for removal of residual cancer is 96%. Thus, the overall study power is $90\% \times 99\% \times 96\% = 86\%$.

Revision note: As of the release of revision 08 of study protocol CL0007, an event count conducted in April 1st, 2021 indicated that 380 patients need to be enrolled to achieve the necessary 70 truth standard positive events. We now intend to enroll up to **450** subjects in this study.

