4.5 Study sample size, event-driven design, and overall study power

The pivotal study is powered based upon targeting success for the three co-primary endpoints as outlined above. The efficacy endpoints will be assessed in the patients who undergo LUM-guided imaging (not the 1/10th of subjects randomized to the control arm).

Based on Phase C data, it is expected that 268 patients will provide the necessary 70 truth standard positive events to power for sensitivity. Also, based on Phase C data, it is expected that 152 patients will provide the necessary 1021 truth standard negative events to power for specificity. To power for the removal of residual cancer endpoint, approximately 220 patients are required. Thus, the size of this study is driven by the necessary number of truth standard positive events.

Adding 15% to the sample size of 268 patients to include subjects in the control arm and some expected data loss, it is estimated that 310 total patients will be needed for the pivotal study. However, given the uncertainty of translating the number of truth standard positive events to actual number of patients, the pivotal trial is planned as event-driven clinical study. Patients will be enrolled until 70 truth standard positive events are reported, up to a maximum of 450 patients. The number of truth standard positive events will be counted based on the truth standard hierarchical approach from Figure 2. Counting of these events will be conducted via software programming to read from the electronic data capture system; no endpoints will be calculated at that time. Results from the event counting process will be accessible to the DSMB which will then inform Lumicell

LUMICELL CONFIDENTIAL

This document is confidential. Do not disclose or use except as authorized.

personnel on whether the targeted number of events has been reached or if enrollment needs to continue.

With the proposed sample size from sensitivity, under the alternative hypothesis for specificity using the GEE model with a compound symmetry correlation structure, the power to show true specificity above the performance goal of > 60% will be >99%. For removal of residual cancer, the power is estimated at 96%. Thus, the overall study power is $90\% \times 99\% \times 96\% = 86\%$.

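### Residual-cancer power does not follow from the stated inputs: at a 9% rate, 220 patients give 96.4% power, not 90%, and the rate and n behind the 96% in the overall-power product are not stated

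*SAP*

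**What the plan says.** SAP 4.2 sets the null rate at 3% or less and uses an exact binomial test at one-sided 2.5%. The planning rate is given as "we are using a slightly more conservative assumption of a ~9% true percentage of patients", set below the Phase C result of 26/230 (11.3%). On that basis, "enrolling 220 evaluable subjects, a binomial exact test for proportions at a one-sided significance level of 2.5%, will have 90% power". Protocol 15.3.1 makes the same claim: "enrolling 220 evaluable subjects, a binomial exact test for proportions at a 1-sided significance level of 2.5%, will have 90% power".

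SAP 4.5 turns this into a requirement: "To power for the removal of residual cancer endpoint, approximately 220 patients are required". It also says that "it is expected that 268 patients will provide the necessary 70 truth standard positive events to power for sensitivity", and makes sensitivity the driver of study size.

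The overall-power paragraph of SAP 4.5 opens with "With the proposed sample size from sensitivity", gives the specificity power, and continues: "For removal of residual cancer, the power is estimated at 96" per cent. Protocol 15.3.3 puts all three powers in one sentence: "At this sample size, the power for the sensitivity endpoint is 90%, for specificity is 99% and for removal of residual cancer is 96" per cent. Both documents then multiply 90% × 99% × 96% to reach 86%. Neither gives a planning rate or a numeric n beside the 96%.

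**The concern.** Every input to the 90% is stated: the test, the alpha, the null rate, the assumed rate and the number of evaluable patients. The figure should therefore be reproducible, and a threefold ratio of 9% to 3% in 220 patients looks too favourable for only 90%. The second figure, 96%, is what one would expect at 220 patients, yet it appears where the text is discussing a larger study.

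At stake are the stated power and required sample size of one co-primary endpoint, and one factor of the overall power. If the power is wrong, the text understates it. If the planning rate is wrong, the assumption on which the endpoint was powered is misreported.

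**Working it through.** **Inputs.** p0 = 3%, exact binomial, one-sided α = 0.025 (SAP 4.2, 4.6); p1 = about 9%, n = 220 evaluable, stated power 90% (SAP 4.2, protocol 15.3.1); n = 268 for sensitivity, 310 in total, stated residual-cancer power 96% (SAP 4.5, protocol 15.3.3). The 220 are already evaluable, so no loss is deducted.

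**Method.** Take the smallest r with P(X ≥ r | n, 0.03) ≤ 0.025. Power is then P(X ≥ r | n, p1).

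**Check of the method on the protocol's other endpoints (15.3.2).**
- Sensitivity, 70 events, 60% against 40%: reject at 37 or more, power 90.9% (stated 90%).
- Specificity, 1021 events, 65% against 60%: power 90.7% (stated 90%).

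**Attempt to reproduce 90% at n = 220.** P(X ≥ 12 | 0.03) = 0.035 is too large and P(X ≥ 13 | 0.03) = 0.0163 is acceptable, so r = 13. The SAP's confidence-interval rule gives the same cut: the exact lower limit is 2.85% for 12/220 and 3.18% for 13/220.

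| True rate | n = 220 (r = 13) | n = 268 (r = 15, α = 0.0164) |
|---|---|---|
| 8.0% | 90.2% | 94.7% |
| 8.5% | 94.0% | 97.1% |
| 9.0% | **96.4%** | **98.5%** |
| 9.5% | 97.9% | 99.3% |

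No rate that rounds to 9% gives 90% at 220. Nor does another method at 9% and 220: one-sided α 0.0125 gives 93.7%, α 0.05 gives 98.1%, the normal approximation 97.4% (96.6% with continuity correction), arcsine 97.2% and Wald 87.5%. Deducting 15% (220 × 0.85 = 187) gives 91.9%, but the text calls the 220 evaluable.

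**n needed for 90% power.** Exact power is saw-toothed in n, so two values are given.

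| True rate | First reached | Holds at every larger n |
|---|---|---|
| 9.0% | 156 | 169 |
| 8.5% | 179 | 193 |
| 8.0% | 205 | 220 |

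The pair 220 and 90% is what an 8% rate would give. The rate that gives exactly 90% at 220 is 7.98%.

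**Where 96% could come from.** It matches 9% at 220 (96.4%). It also matches 8% at 310 (96.5%), or 8% at 282 (96.8%), where 282 = 310 × 10/11 is an assumed device-arm share. At 268, exactly 96% needs a rate of 8.23%.

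**Overall product, other factors as stated.**
- As printed: 0.90 × 0.99 × 0.96 = 85.5%, shown as 86%.
- 268 patients at 9%: 0.90 × 0.99 × 0.985 = 87.8%.
- 268 at 8.5%: 0.90 × 0.99 × 0.971 = 86.5%.
- 268 at 8%: 0.90 × 0.99 × 0.947 = 84.4%.

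**The case against.** The best reply concerns the 96%. In SAP 4.5 the phrase about the sample size from sensitivity belongs grammatically to the specificity sentence, and protocol 15.3.3 refers to a sample size after naming 268, 310 and 350 patients. If the n is not stated, 96% cannot strictly be called wrong, and at 8.5% and 268 the gap is only about one point. This stands in part: the 96% is the weaker half of the point. But 268 remains the natural reading, since the protocol ties all three powers to one sample size at which sensitivity has 90%, and the product needs a common n.

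Second, 8% appears nowhere in the documents. It is back-solved, and at 268 it gives 94.7%, not 96%. This also stands: 8% is a possible explanation, not a finding about what the sponsor did.

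Third, the consequence is small. The endpoint does not set the study size, and SAP 1.1 already refers to 406 enrolled patients. With an assumed 10/11 device share (406 × 10/11 ≈ 369, before exclusions), power is 99.8% at 9% and 98.7% at 8%. This limits the weight of the point but does not correct the text.

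Fourth, the check against the other two endpoints covers the protocol's exact binomial figures, not the SAP's GEE simulations with an ICC of 0.22. That is correct. The residual-cancer endpoint is one result per patient and is tested by the exact binomial in both documents.

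None of these replies explains 90% at 220 and 9%.

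**Conclusion.** The concern holds. Under the stated test and a 9% rate, power at 220 evaluable patients is 96.4%, which is 6.4 points above the stated 90%. Even at 8.5% it is 94.0%. The requirement of about 220 patients exceeds what 9% calls for by roughly 50 to 65 (220 − 169 = 51; 220 − 156 = 64).

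The 96% in the product has no stated rate or n. If it refers to 268 patients, it is 2.5 points low at 9% and 1.3 points too high at 8%. The overall power is then 87.8% or 84.4%, against 85.5% as printed.

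At the stated rate the error is conservative and changes no decision: enrolment is driven by 70 truth standard positive events, and the test and the 3% goal are untouched. This is a minor point of reproducibility. It rests on the exact binomial test as specified, on 220 being evaluable patients and, for the second figure only, on reading the 96% at 268.

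**What to change.** In protocol 15.3.1 and 15.3.3 and SAP 4.2 and 4.5, state the planning rate and the n beside each residual-cancer power, and make the figures agree. The sponsor needs to confirm which rate was used.

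- If 9% is the planning rate: state 96.4% at 220 and 98.5% at 268, give about 169 patients as the number needed for 90%, and show the overall power as about 88%.
- If the calculation in fact used 8%: correct the stated rate, keep 90.2% at 220, state 94.7% at 268, and show the overall power as about 84%.

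The value carried into the overall-power product should be the one for the same n as the other two factors.

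The cost is wording in two documents. Enrolment, the test and the success rule do not change.

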4.3 Per tissue sensitivity and specificity (co-primary endpoints)

4.3.1 Analysis methods and inpatient correlation

Three separate analyses will be conducted for sensitivity and specificity assessment. The first analysis uses the Binomial estimator and the other two approaches address potential intra patient correlations.

- Binomial estimator: the probability and the confidence interval are estimated according to binomial distribution

LUMICELL CONFIDENTIAL

This document is confidential. Do not disclose or use except as authorized.

- Generalized Estimating Equation (GEE): This method is used to analyze correlated data which is modeled with generalized linear model having binomial link function, and including correlation cluster and matrix information (here within each subject). Procedure Genmod in SAS is used to apply this method (<https://support.sas.com/rnd/app/stat/topics/gee/gee.pdf>). This method with a compound symmetry working correlation structure, will be used to estimate sensitivity and specificity along with a 97.5% lower bounded one-sided confidence interval (CI) (* Tessa S. S. Genders, Sandra Spronk, Theo Stijnen, Ewout W. Steyerberg, Emmanuel Lesaffre, M. G. Myriam Hunink. Methods for Calculating Sensitivity and Specificity of Clustered Data: A Tutorial Radiology: Volume 265 (3):910 (2012)).
- Bootstrapping sampling method: This method is applied to sample the subjects with replacement at the same sample size of mITT for 10,000 rounds. The sampled subjects with corresponding imaging, and standard truth positive and negatives will be used to estimate the sensitivity and specificity. The median sensitivity and specificity will be used as the estimate from bootstrapping method. The 2.5% and 97.5% percentiles will be used as lower and upper bounds, respectively, for 95% confidence intervals.

4.3.2 Performance goals

The verification of the sensitivity and specificity co-primary endpoints will be a refutation of the null hypotheses

$$H_{01}^s: sen \leq 40\% \text{ against the alternative } H_{11}^s: sen > 40\%$$

$$H_{02}^s: spec \leq 60\% \text{ against the alternative } H_{12}^s: spec > 60\%$$

where *sen* and *spec* represent the true sensitivity and specificity, respectively. The hypotheses involving sensitivity and specificity will be assessed based on the data collected per-tissue level.

These hypotheses will be tested using a one-sided significance level of 2.5%. To account for within-subject correlation, Generalized Estimating Equations (GEE), with a compound symmetry working correlation structure, will be used to estimate sensitivity and specificity along with an equi-tail 95% two-sided confidence interval (CI). The null hypothesis H_{01}^s is rejected if the lower bound of the confidence interval for sensitivity is larger than the performance goal of 40%. Similarly, the null hypothesis H_{02}^s is rejected if the lower bound of the confidence interval for specificity is larger than the performance goal of 60%.

Performance Goals selection for sensitivity and specificity endpoints

Data from the Phase C Feasibility Study showed pathology margin assessment sensitivity to predict cancer in the cavity of ~40%. However, this pathology assessment is done several days after the surgery and can lead to second surgeries. Because the LUM Imaging System provides the additional benefit of assessing the cavity in real-time, a performance goal for instrument sensitivity > 40% is proposed as the success criterion for this hypothesis-tested endpoint. We expect the sensitivity to be similar to that observed in the Phase C study of 69% [95% CI: 56%-80%].

LUMICELL CONFIDENTIAL

This document is confidential. Do not disclose or use except as authorized.

The Phase C data shows that at the current specificity performance of 70% [95% CI: 68%-73%], an average of 1.1 additional shaves were removed guided by the LUM Imaging system, accounting for ~10% of all the total resected tissue. We selected a performance goal for specificity of > 60% to ensure that similar performance in the pivotal trial is obtained regarding tissue removal. Also, with this lower bound, a Youden Index > 0 will be demonstrated to indicate non-random diagnostic performance.

Sample size for testing sensitivity:

As sensitivity and specificity are estimated at the per tissue level, within subject correlation is considered for the sample size estimation. Intraclass Correlation Coefficient (ICC) was estimated with data from the Feasibility Phase C study. The ICC value was obtained at 0.145 for the full phase data set and at 0.22 for the validation data set which the tumor detection algorithm is same as that used in the pivotal study. We selected ICC at 0.22 for sample size estimation.

The parameters for the simulation is as below:

- True sensitivity is 60%
- Intraclass Correlation Coefficient (ICC) value = 0.22
- Truth standard positive rate 4%
- Performance Goal (PG) = 40%
- 2.5% one-sided significance level
- 70 truth standard positive shaves

Assuming 70 truth standard positive shaves, under the alternative hypothesis, using Generalized Estimating Equation (GEE) model with a compound symmetry working correlation structure, will have >90% power to show that the true sensitivity is > 40%.

Sample size for testing specificity:

The parameters for the simulation is as below:

- True specificity is 65%
- Intraclass Correlation Coefficient (ICC) value = 0.22
- Truth standard negative rate 96%
- Performance Goal (PG) = 60%
- 2.5% one-sided significance level

Under the alternative hypothesis, using Generalized Estimating Equation (GEE) model with a compound symmetry working correlation structure, 1023 truth standard negatives are needed to reach >90% power to show that the true specificity is >60%.

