1.1 Considerations for integrated safety analysis and integrated efficacy analysis

For the pivotal trial clinical study report, safety data will be presented from the 406 patients enrolled in the study. However, for the Integrated Summary of Safety (ISS for NDA submission) and the Summary of Safety and Efficacy (SSE for PMA submission) we plan to include safety data from patients that have been injected with LUM015 across multiple indications. This integrated safety analysis will be detailed in the statistical analysis plan for the ISS.

2 Analysis Populations

- Safety (SAF) Population: the safety population includes all subjects who received study drug (LUM015).
- Modified Intent To Treat (mITT) population: includes the subjects in SAF, but excluding subjects who are not able to be imaged with the LUM Imaging System. That is, the mITT population includes all patients imaged with the LUM Imaging System and will be used as the primary analysis population for the three co-primary efficacy endpoints and efficacy analysis of the secondary endpoints.
- Per-Protocol Population: Includes mITT subjects who complete all study evaluations and are without any major protocol deviations that may impact data collection or efficacy analysis. A sensitivity analysis of the primary and secondary efficacy endpoints will be conducted using the per-protocol analysis set.

3 Study endpoints

The pivotal trial will have three co-primary endpoints and other secondary endpoints, which are summarized in the next sections.

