4.4 Per patients sensitivity and specificity (secondary endpoint)

Based on feedback from FDA, Lumicell is including an analysis of sensitivity and specificity at the patient level. Because a single patient can have up to 6 lumpectomy cavity orientations, each orientation with its own image, there will be patients that can have truth standard negatives and truth standard positives within the cavity. Thus, we propose to evaluate the per-patient truth standards as described below.

LUMICELL CONFIDENTIAL

This document is confidential. Do not disclose or use except as authorized.

Definitions for per-patient truth standards:

- Truth standard positive patient: a patient having at least one orientation as a truth standard positive using the per-tissue hierarchical approach
- Truth standard negative patient: a patient having all orientations as truth standard negatives using the per-tissue hierarchical approach.

Definitions for per-patient Lumicell imaging results:

- Positive detection patient by Lumicell imaging device: Lumicell device detects at least one positive signal in a patient
- Negative detection patient by Lumicell imaging device: Lumicell device does not detect any positive signal in a patient; that is, all Lumicell signals for that patient are negative.

Using these definitions, the per-patient 2x2 contingency table will be populated as:

- True positives: truth standard positive patients with positive detection by Lumicell imaging device
- True negatives: truth standard negative patients with negative detection by Lumicell imaging device
- False negatives: truth standard positive patients with negative detection by Lumicell imaging device
- False positives: truth standard negative patients with positive detection by Lumicell imaging device

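### The SAP's specificity sample size and power are stated for ICC 0.22 but are the independent-tissue answers, so the 86% overall power is unsupported

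*SAP*

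**What the plan says.** SAP 4.3.2 accepts that tissues within a patient are correlated. It reports Phase C estimates of 0.145 (full data set) and 0.22 (validation set) and states "We selected ICC at 0.22 for sample size estimation". The specificity simulation inputs are true specificity 65%, performance goal 60%, one-sided 2.5%, ICC 0.22 and "Truth standard negative rate 96" percent. Under GEE with compound symmetry it concludes that "1023 truth standard negatives are needed to reach >90% power to show that the true specificity is >60" percent. The decision rule is the GEE interval: the null "is rejected if the lower bound of the confidence interval for specificity is larger than the performance goal of 60" percent.

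SAP 4.5 says "it is expected that 152 patients will provide the necessary 1021 truth standard negative events to power for specificity", and that at the size set by sensitivity (268 patients) "the power to show true specificity above the performance goal of > 60% will be >99" percent. It multiplies 90% x 99% x 96% to reach 86% overall.

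Protocol 15.3.2 derives 1021 negatives for 90% power from an exact binomial test without any correlation, and names that test as the hypothesis test. Protocol 15.3.3 gives the same 99% and 86%.

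**The concern.** Moving from independent tissues to ICC 0.22 changes the requirement by two tissues, from 1021 to 1023. That can happen only if almost every patient contributes a single negative. The documents say otherwise: SAP 4.5 puts 1021 negatives in 152 patients, and SAP 4.4 notes that "a single patient can have up to 6 lumpectomy cavity orientations". With several correlated tissues per patient, the effective sample size must fall well below the count.

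Specificity is a co-primary endpoint that has to succeed, and its stated power enters the overall power. If the correlation was listed but not applied, three claims lose their support: that 152 patients suffice for specificity, that its power exceeds 99%, and that overall power is 86%.

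**Working it through.** **Inputs.** Specificity 65% against 60%, one-sided 2.5%, ICC 0.22 (SAP 4.3.2); 268 imaged patients (SAP 4.5); 380 projected and a cap of 450 (protocol 15.3.3); "safety data will be presented from the 406 patients enrolled in the study" (SAP 1.1); 10:1 randomization (protocol 5.2.7).

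**Negatives per patient, m.** No distribution is given, so a range is derived:
- SAP 4.5: 1021/152 = 6.72.
- SAP 4.3.2 rates: 70 positives/0.04 x 0.96 = 1680 negatives; 1680/268 = 6.27.
- SAP 4.4: up to 6 orientations, so m = 6 as a lower scenario.

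**Step 1. Reproduce the stated figures with ICC = 0 (exact binomial).**

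| Negatives | Power |
|---|---|
| 1020 | 89.9% |
| 1021 | 90.7% |
| 1023 | 91.0% |
| 1680 (268 x 6.27) | 98.8% |
| 1800 (268 x 6.72) | 99.1% |

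The stated figures match independence.

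**Step 2. Apply ICC 0.22 by formula.** Design effect DE = 1 + (m - 1) x ICC; effective n = n/DE; power = Φ(δ√(n_eff x 0.65 x 0.35) - 1.96), with δ = logit(0.65) - logit(0.60) = 0.2136.

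| m | DE | n_eff at 1023 | Power | n_eff at 268 patients | Power |
|---|---|---|---|---|---|
| 6 | 2.10 | 487 | 61% | 766 | 81% |
| 6.72 | 2.26 | 453 | 58% | 797 | 82% |

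Score and Wald versions differ by at most about 3 points.

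**Step 3. Check by simulation.** Beta-binomial clusters, intercept-only logit GEE, exchangeable correlation, sandwich variance, 20,000 replicates. At 1023 negatives, power is 58.3% as 152 patients and 61.9% as 170 patients with 6 each. By number of imaged patients:

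| Device-arm patients | m = 6 | m = 6.27 | m = 6.72 |
|---|---|---|---|
| 268 | 81.2% | 81.7% | 82.8% |
| 345 (380 x 10/11) | 89.4% | 90.0% | 90.7% |
| 369 (406 x 10/11) | 91.8% | 92.1% | 92.5% |
| 409 (450 x 10/11) | 94.2% | 94.4% | 95.0% |

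Uneven clusters of 3 to 10 (mean 6.5) give 81.2% at 268 patients and 91.6% at 369.

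**Step 4. What would restore the stated figures?** At m = 6.72, power at 152 and 268 patients is 90.3% and 99.1% for ICC 0.005, but 89.4% and 98.9% for ICC 0.01. So an ICC of about 0.005 or less is needed. The milder Phase C value of 0.145 gives 67% and 89%. With only 3 negatives per patient, 1023 gives about 79%. One negative per patient gives 91.1%, but needs 1023 patients against a cap of 450.

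**Step 5. Size for 90%.** 1021 x 2.10 = 2144 negatives, /6 = 357 patients; 1021 x 2.258 = about 2306, /6.72 = 343 patients. The plan says 152.

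**Step 6. Overall power by the plan's product rule.**
- At 268, with the plan's 90% and 96%: 0.90 x 0.81 to 0.83 x 0.96 = 70-72%.
- The 96% is the exact residual-cancer power at 220 patients (96.4%). At 268 it is 98.5%, giving 72-74%.
- If sensitivity is also clustered (70 positives, ICC 0.22: 90.5% for 46 singles and 12 pairs, 86.2% for 35 pairs; both patterns assumed), then with 96% the product is 67-72%.
- At 369, with residual-cancer power 99.8%: 0.90 x 0.92 to 0.93 x 0.998 = about 83%.

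**The case against.** The strongest reply is that 268 patients is no longer the operative size. The trial is event-driven, the protocol's revision note moves to 380 patients and a cap of 450, and 406 were enrolled. At about 369 device-arm patients specificity power is 92-93% and overall power about 83%, some 3 points below 86%. This stands as to practical effect, but the documents still state >99% and 86%, and neither is reached at that size.

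The SAP also does not say on which scale the ICC is defined. If 0.22 is a latent-scale value, the binary ICC is about 0.13; power is then about 67-74% at about 1020 negatives and 89-91% at 268 patients. The 58-62% and 81-83% are therefore conditional on the usual binary-scale reading. The mismatch survives either way.

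The match of >99% to independence is exact only at 6.72 negatives per patient; at 6.27 it is 98.8% and at 6 it is 98.5%. This is a small difference beside 81-83%.

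The protocol's binomial test may be thought harmless because the protocol defers detail to the SAP, whose GEE rule is clear. That is largely right, and the point is secondary. Two documents should still not name different deciding tests when, at ICC 0.22, the binomial test's one-sided error is about 8-9% instead of 2.5%.

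Finally, if true specificity is near Phase C's 70%, power at 268 patients is above 99.9%. The stated figures, however, are explicitly for 65%.

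**Conclusion.** The concern holds. The SAP reports independent-tissue results as if they were computed at ICC 0.22. At its own inputs, 1023 negatives give about 58-62% power (stated >90%) and 268 patients about 81-83% (stated >99%). Power above 99% is not reached even at the 450 cap (94-95%). About 343-357 device-arm patients are needed for 90%, not 152.

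This rests on 6 to 6.7 negatives per patient (derived, since no distribution is given), a binary-scale ICC, the 10:1 ratio and no loss of imaged patients. The overall figures also follow the plan's product rule, which treats the three endpoints as independent. The direction does not depend on the first two assumptions: neither 3 negatives per patient nor a latent-scale ICC restores the stated values.

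The 90% target for specificity is met at the enrolled size, so the damage is to the stated justification of a co-primary endpoint, not to the adequacy of enrolment. It should be fixed.

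**What to change.** 1. Rerun the specificity simulation at ICC 0.22, stating the distribution of truth-standard negatives per patient and the scale of the ICC.
2. Replace 1021/1023, 152 patients, >99% and 86% in SAP 4.3.2 and 4.5 and protocol 15.3.2 and 15.3.3. Show power at 268 imaged patients, at the enrolled 406 and at the 450 cap.
3. Recompute overall power at each size, with the ICC applied to sensitivity and the residual-cancer power taken at the same size.
4. Align protocol 15.3.2 with SAP 4.3.2, so that the GEE lower bound is the deciding test and the binomial estimator is supportive.

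The cost is one simulation rerun and wording changes in two documents. No patients are added and the SAP's success rule stays as it is; the stated power becomes less favourable.
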